We have been implementing the study according to this plan and have had 4 waves of recruitment at Horizon House, 5 at Neponset River House, and 3 at Eliot House for a total of 12 waves of recruitment. However, recruitment has been slowing down and we are unable to enroll approximately 16 individuals per wave as was planned. We had previously discussed a backup plan with Riverside leadership to extend the study to their clubhouse in Hopedale in the event that recruitment slowed down and we were not able to meet target recruitment. At this time, we would like to implement this plan. We have approval from the sponsor, NIMH, to proceed with this plan. The procedures at Hopedale will remain the same as they have been at the other clubhouses.

We worked with Riverside senior management to establish the non-overlapping number of clients with SMI served in the catchment areas for the three clubhouses where the Photovoice program will be offered. About 1,300 individuals with SMI are served on an annual basis in the three catchment areas (Norwood, Needham and Wakefield) where the study will be conducted; of them, approximately 900 individuals are served by the clubhouses and the CBFS teams, all of whom meet MA criteria for SMI, with approximately 50% diagnosed with a schizophrenia-spectrum disorder. Riverside treats approximately 200 new clients with SMI per year, with most being served at the clubhouses or by CBFS teams. Thus, there are an ample number of eligible participants for the study. Furthermore, in our pilot feasibility study at the Norwood clubhouse, 8 (53%) out of the 15 participants had a diagnosis of schizophrenia-spectrum disorder.

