When a referral using the Consent to Contact form is made to the project, the potential participant will be contacted by phone or in person by the Project Coordinator to further determine their understanding of the research and their interest in participation. Prior to the phone call the Project Coordinator will obtain information about the person's diagnoses, including history or diagnosis of intellectual disability. In case an interested individual has a diagnosis associated with intellectual disability, the Project Coordinator will contact this person and inform him/her that they don't meet the study eligibility criteria based on information in their chart record. The Project Coordinator will explain the following to interested individuals who meet diagnostic eligibility: the details of the study, random assignment to two conditions, the interventions, and the research interviews as well as provisions for maintaining privacy and confidentiality. The Project Coordinator will screen for inclusion and exclusion criteria during this initial contact. Thus, all screening will be completed prior to administration of informed consent without implications for participants' compensation; hence, no references to pre-consent screening are included in the ICF. If the person remains interested in the study, the Project Coordinator will set up an appointment for the informed consent. If a person has a legal guardian, the guardian will be involved in the consent process. For those individuals who do not have a guardian, the Project Coordinator will explain the study in person and ask a brief set of questions to determine whether the individual has understood the nature of the research project, including the assessments and treatment approaches. We will provide corrective information as needed if the individual is unable to answer the quiz questions during the consent process, followed by additional checking to assure a participant's full and knowing consent. Potential participants who continue to express interest in the study and are able to demonstrate their understanding of the study by correctly answering these questions will then be asked to sign the informed consent form. Individuals who meet the eligibility criteria and who are able to provide full and knowing consent will proceed to scheduling of the baseline assessment with the Clinical Interviewer. Upon completion of the baseline assessment, participants will be randomly assigned to either the experimental (Photovoice) or the enhanced Services as Usual (SAU) conditions. The Project Coordinator will contact each participant and explain their randomization condition. Participants randomized to participate in the Photovoice program will be informed about the date of their first Photovoice session and participants randomized to the control condition will be informed about the date of the 60-minute peer-led group discussion session about understanding and coping with prejudice and discrimination. The Clinical Interviewer will be blind to participants' randomization.

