month and 6-month post-treatment follow-ups by the Clinical Interviewer who will be blind to the participant randomization status. The Clinical Interviewer will be trained in methods for eliciting self-report information, and standard interviewing procedures. In order to ensure high reliability and prevent rater drift of the Clinical Interviewer, we will audiotape all assessments and we will randomly select 10-15% for reliability checks. We will collect all relevant service utilization information from Riverside using their administrative databases after participants have completed the 6-month follow-up assessment. Eligible individuals who consent to participate at the study will complete a second Riverside Release of Information (ROI) form to authorize release of service utilization data since the first ROI will authorize only release of their chart diagnoses to determine eligibility.

We will be using the following measures to assess these outcomes:

Mini Neuropsychiatric Interview (MINI) - is a widely used 15-minute structured interview assessing the presence of 17 DSM-IV Axis I disorders with good concordance with the SCID and the CIDI and with acceptable test-retest reliability.

Brief Psychiatric Rating Scale - is a 24-item scale that rates severity of a variety of psychiatric psychotic symptoms, positive and negative symptoms on a 7-point scale of 1 (absent) to 7 (severe).

Approaches to Coping with Stigma - (Link et al., 1989) – is a 27-item, 4-point scale (strongly disagree to strongly agree) measuring strategies to cope with stigma: secrecy, withdrawal, distancing, educating others, and challenging others. The total score of the first three subscales will represent the index for Avoidant Coping and the total score of the last two subscales – the index for Proactive Coping with Stigma. Internal consistency for subscales range: .63-.84.

Internalized Stigma of Mental Illness Scale - a 29-item, 4-point scale (strongly disagree to strongly agree) assesses behaviors, thoughts and feelings that are self-stigmatizing and includes alienation, stereotype endorsement, discriminatory experiences, social withdrawal, and stigma resistance subscales. Internal consistency is .9 and test-retest reliability is .92.

The Stigma Scale (King et al, 2007) - is a 28 item, 5 point scale (strongly disagree to strongly agree) measuring experienced and anticipated stigma. Internal consistency ranges from .85-.87 and test-retest reliability from .4 to .7.

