Heinrich's Quality of Life Scale-Client Version - Is a 21 item semi-structured interview based rating of individual's psycho-social functioning and satisfaction with various life domains.

Temple University Community Participation Scale - is a 26 item instrument measuring frequency of participation and importance of various community activities (e.g., movies, library). Test-retest reliability is .7 and internal consistency is .9.

Scales of Psychological Well-Being - is a 54-item measure rating wellbeing (from strongly disagree to strongly agree) including subscales of mastery, personal growth, purpose in life, self-acceptance, autonomy and positive relations with others. Internal consistency is .94. It has been successfully used with individuals with SMI.

Maryland Assessment of Recovery - is a 25-item scale that assesses a person's sense of recovery from mental illness across a variety of dimensions. Internal consistency is .95 and test-retest reliability is .89).

Personal Growth and Recovery Scale - (BU CPR, 2009) - is a 16-item, 4 point scale (strongly disagree to strongly agree) developed for previous Photovoice study. Items tap aspects of person's psychosocial functioning and recovery. Internal consistency is 0.94 and retest reliability is .79.

Photovoice Program Fidelity Scale - the Photovoice Fidelity Scale was developed and used in our pilot RCT study (Russinova et al., 2014). The scale includes content fidelity items specific to each of the 10 Photovoice sessions and 13 process fidelity items which are specific to the Photovoice program as a whole. All items are measured on a 4-point scale from 1, "strongly disagree" to 4, "strongly agree". All Photovoice sessions will be audiotaped and fidelity will be assessed based on review of all audio-recorded sessions.

We will use a **Demographic Questionnaire** developed by the Boston University Center for Psychiatric Rehabilitation and previously used in multiple research studies. Questions inquire about the person's demographic characteristics, such as age, race, gender, education, employment status, housing situation, and basic clinical characteristics, such as perceived physical health and use of different mental health services in the past 3 months. We are using an abbreviated version of this questionnaire at post-treatment and follow-up assessments to capture information only on time varying variables included in the questionnaire.

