Testing Effectiveness of a Peer-Led Intervention to Enhance Community Integration

NCT02508480

Statistical Analysis Plan

Date: July 24th, 2019

Statistical Analysis Plan-

Intent-to-treat analyses will be conducted on the full sample of participants, regardless of actual exposure to the Photovoice program. Based on our pilot RCT study of Photovoice we are confident that majority of participants randomized to the Photovoice group will receive the intervention. However, if significant rates of non-exposure occur, we will also conduct separate analyses on treatment exposed participants. The intent-to-treat sample will include all participants for whom we have baseline data. It assumes that participants who are not exposed to the Photovoice program are not also study dropouts, and thus the analyses will include all available study participants. These analyses are the primary gauge of the effectiveness of the Photovoice program. If dropout rates from the Photovoice group exceed 20% we will explore the question of treatment effectiveness for those who participated in the Photovoice program. Participants will be classified based on their level of participation, with "exposure" defined as attendance at more than one-half of the 10 sessions (6 or more), with parallel analyses comparing the exposed Photovoice group with SAU. We will test the following primary hypotheses:

Hypothesis 1: Compared to SAU, clients randomized to the Photovoice program will demonstrate significantly greater improvements at post-treatment and 3- and 6-month follow-ups in their capacity to resist public prejudice and discrimination, including reduced self-stigma and perceived stigma, and increased proactive coping with public prejudice and discrimination (e.g., confronting prejudicial and discriminatory attitudes and behaviors). We will test this hypothesis by using the total score on the Internalized Stigma of Mental Illness Scale⁷⁸ and on the Stigma Scale⁹³, and the sum of the two proactive coping subscales on the Coping with Stigma Scale (Educating Others, Challenging Others)⁹² and fitting covariance pattern models (using SAS PROC MIXED) and examining time (baseline, post-treatment, 3- and 6 month follow-ups), group, and the group by time interaction effects.

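### The mixed model gives each arm its own baseline mean although baseline precedes randomization: valid, but precision is lost, and the SAP does not name the deciding test

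*SAP*

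**What the plan says.** Under Hypothesis 1 the SAP plans covariance pattern models in PROC MIXED. It gives the model terms as "examining time (baseline, post-treatment, 3- and 6 month follow-ups), group, and the group by time interaction effects". It mentions no baseline constraint and no baseline covariate. It names none of the three effects as decisive and gives no alpha or sidedness. Hypothesis 2 names the Temple University Community Participation Scale as outcome but states no model or test.

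On the analysis set, the SAP says: "The intent-to-treat sample will include all participants for whom we have baseline data".

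The protocol's recruitment text (before section 7) fixes the order of events: "Upon completion of the baseline assessment, participants will be randomly assigned". The same part of the protocol gives 192 participants, 96 per arm, and reports that "recruitment has been slowing down and we are unable to enroll approximately 16 individuals per wave as was planned". It then adds a further clubhouse as the remedy.

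Protocol section 7 gives the only figures that bear on correlation between visits:
- Internalized Stigma of Mental Illness Scale: "Internal consistency is .9 and test-retest reliability is .92".
- Stigma Scale: "Internal consistency ranges from .85-.87 and test-retest reliability from .4 to .7".
- Temple participation scale: "Test-retest reliability is .7 and internal consistency is .9".

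**The concern.** Four visits by two arms, with group and group-by-time both in the model, make eight free means. Two of them are baseline means, one per arm. Because nobody is allocated before the baseline assessment is complete, those two have the same expectation. Estimating them separately makes each treatment effect a difference in change from baseline, which carries the full sampling noise of the baseline difference.

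This is a loss of efficiency and not a bias. The 3-df interaction does test differences in change. But the lost precision could be had from data already collected, in a trial that reports recruiting below plan.

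The second gap is the missing decision rule. The hypothesis speaks of greater improvement, which points to the interaction, but the SAP does not commit to it. A group main effect averaged over four visits includes the pre-treatment visit. It therefore targets only three quarters of a constant effect.

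**Working it through.** **What can be reproduced.** The documents give no power calculation, so there is no power figure to reproduce. The sample-size arithmetic is consistent: 12 cohorts × 16 = 192, and 192/2 = 96 per arm.

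**Inputs.** From the documents: n = 96 per arm, four visits, baseline before allocation. Assumed: unit SD, complete data, the same correlation rho between any two visits, no clustering, two-sided alpha 0.05. The retest values are only a guide to rho.

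**Variance of one visit contrast.**
- Free baselines: (2/n) × 2(1 − rho).
- Common baseline: (2/n) × (1 − rho²).
- Ratio: (1 − rho²) / [2(1 − rho)] = (1 + rho)/2.

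At rho = 0.4: (2/96) × 1.2 = 0.0250, so the 95% half-width is 1.96 × √0.0250 = 0.31 SD. With a common baseline, (2/96) × 0.84 = 0.0175, giving 0.26 SD. To match this, the free model needs 96/0.70 = 137 per arm.

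| rho | variance ratio | half-width, free | half-width, common | n per arm for free model to match |
|---|---|---|---|---|
| 0.4 | 0.70 | 0.31 | 0.26 | 137 |
| 0.6 | 0.80 | 0.25 | 0.23 | 120 |
| 0.7 | 0.85 | 0.22 | 0.20 | 113 |
| 0.92 | 0.96 | 0.11 | 0.11 | 100 |

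**Power of the joint 3-df test.** Power comes from the noncentral chi-square with 3 df (critical value 7.81). For a constant effect d the noncentrality is:
- Free: n d² × 0.75 / [2(1 − rho)].
- Common: n d² × 3 / [2(1 − rho)(1 + 3 rho)].

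At d = 0.3 and rho = 0.4: free = 96 × 0.09 × 0.75 / 1.2 = 5.40, power 47%. Common = 96 × 0.09 × 3 / (1.2 × 2.2) = 9.82, power 75%. Other effect shapes use e′ cov⁻¹ e with the same matrices.

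| Effect | rho 0.4 | rho 0.6 | rho 0.7 |
|---|---|---|---|
| constant 0.2 SD | 22.5 → 38.9% | 32.5 → 45.2% | 42.4 → 53.2% |
| constant 0.3 SD | 47 → 75% | 66 → 83% | 80 → 90% |
| constant 0.4 SD | 74.2 → 95.3% | 90.5 → 97.8% | 97.0 → 99.3% |
| 0.3 SD at first, half at 3 months, none at 6 | 44 → 52% | 62 → 67% | 76 → 79% |
| 0.3 SD at one visit only | 47 → 51% | 66 → 68% | 80 → 81% |

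At rho 0.92 and 0.3 SD both tests are near 100%.

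**Sensitivity, constant 0.3 SD, rho 0.4/0.6/0.7.**
- Assumed cumulative dropout of 10/15/20% at the three follow-ups, at random: 43.9/61.3/74.7% → 68.4/76.5/84.6%.
- AR(1) correlation: 37/50/62% → 70/71/76%.

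**Validity.** In 200,000 simulated trials per cell with known covariance, type I error was 5.0–5.1% for both 3-df tests.

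**Why the deciding test matters.** Take the planned model, rho 0.5 and a constant 0.4 SD effect. The 3-df interaction has 82% power and the group main effect 75%. If a significant contrast at any one visit sufficed without adjustment, the false-positive rate would be about 12.5% per outcome.

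**The case against.** A covariance pattern model with baseline in the outcome vector is conventional and unbiased, so the alternative can be called a refinement. That is true, and it sets the weight of the point: the reason to change is that the gain costs nothing.

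The size of the gain rests on a correlation the documents do not give. Retest values are quoted without an interval and are not correlations over the roughly 34 weeks of participation. For the Internalized Stigma scale, .92 suggests a negligible gain. For proactive coping no retest value is given. The Temple scale belongs to Hypothesis 2, for which no model is stated. Among Hypothesis 1 outcomes, only the Stigma Scale has a stated value that points to a material gain. All of this stands and limits the claim.

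The large power gains need a sustained effect. For a fading or one-visit effect at rho 0.7 the gain is only 1 to 4 points. This also stands.

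Ignoring clustering flatters the gain. Suppose each of 12 Photovoice groups carries a persistent post-baseline variance of 0.05 SD² (assumed). This adds 0.05/12 to every element of both covariance matrices. At rho 0.4 and a constant 0.3 SD, power goes from 39% to 57% instead of 47% to 75%. With 0.10 SD² it goes from 33% to 45%. The gain shrinks but remains.

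Finally, a hypothesis about greater improvement already implies the interaction, and the time main effect compares no arms. So the decision-rule gap is a clarification, though a needed one.

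**Conclusion.** The concern holds. The planned model is valid but ignores an equality of baseline means that randomization guarantees. With rho between 0.4 and 0.7 the variance of each visit contrast could be 15 to 30% lower, equivalent to adding 17 to 41 participants per arm to the planned analysis (113 − 96 and 137 − 96). The gain in power is large for a sustained effect, modest for a fading one, and negligible where rho is near 0.92. These figures assume 96 per arm, complete data, compound symmetry, no clustering and two-sided 0.05; effect sizes and rho are illustrative.

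The model criticism is documented for Hypothesis 1 only; for Hypothesis 2 the gap is that no model is stated. The change should be made, but the trial's validity does not depend on it.

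**What to change.** In the same PROC MIXED model, constrain the arms to a common baseline mean: time effects plus group-by-visit terms at the three post-baseline visits only. Keep baseline in the outcome vector, so that everyone with baseline data stays in the analysis, as the intent-to-treat definition requires.

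State that the joint 3-df test of the group-by-post-baseline-visit terms decides each hypothesis, and that the group main effect does not. Give its alpha. Report the three visit-specific differences with confidence intervals. Say whether the same model applies to Hypothesis 2.

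The cost is SAP wording and one MODEL statement. The constraint requires every baseline to be taken before allocation, as the protocol states; this should be confirmed from assessment and randomization dates.

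A 1-df average over the three visits is an option only if a sustained effect is expected. At rho 0.4/0.6/0.7, for a 0.3 SD effect gone by 6 months, it has 35/40/46% power against 44/62/76% for the existing test. For an effect at one visit only it has 18/21/24% against 47/66/80%.
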